## 7.2 Evaluations During Intervention\*

- Multiparametric MRI obtained at the University of Miami (+/-) 3 months of enrollment and at 12, 24, and 36 months from initial protocol prostate biopsy.

- MRIus-guided biopsies will be obtained at 0 to 3 months from enrollment (“initial biopsy”) and at 12, 24 and 36 month from initial biopsy.
- History and physical at the discretion of the treating physician. Treating physician can be outside of UM..
- Serum PSA will be done preferably every 6 months or at least once a year up to 36 months from the initial biopsy. If the subject progress, PSA should be done every 6 months (+/- 3 months) or at the discretion of the clinician for the first 3 years and then annually thereafter (+/-6 months) for up to 5 years post treatment.
- If possible, plasma and/or serum (up to 5 tubes) for research purposes (biomarkers) may be obtained at 0 to 3 months from enrollment and at 12, 24, and 36 months from initial biopsy (optional - patient may refuse),
- If possible, post prostate-massage urine (approximately 50 mL) may be collected for research purposes at 0 to 3 months from enrollment and at 12, 24, and 36 months from initial biopsy (optional - patient may refuse). Urine research collection will not be done if research funds are not available.
- Quality of Life surveys obtained 0 to 3 months after enrollment and every 12 months from initial biopsy:
  - Expanded Prostate Cancer Index Composite Questionnaire (EPIC+SF12)
  - Memorial Anxiety Scale for Prostate Cancer patients (MAX-PC)
  - Optional - Food Frequency Questionnaire (FFQ) will be collected only atbaseline.

*\* Follow-up evaluations and visits may occur  $\pm$  1.5 months around each scheduled 6-month timepoint. For example, for the 6 month follow-up, the patient may be seen anytime between 4.5 and 7.5 months from the time of the first prostate biopsy. For the 12-month follow-up, the patient may be biopsied between 10.5 and 13.5 months from the time of the first prostate biopsy. Since the first biopsy may be from between 0-6 months from the day the patient is enrolled, each subsequent calendar event is timed in reference to the time of that first biopsy.*

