## 10.1 Primary Study Endpoints

### 10.1.1 Progression

The main study endpoint will be the 24-month cumulative progression rate. In the context of this trial, progression refers to a repeat surveillance biopsy indicating any one of the following: (i) more than 4 positive cores involving any grade of cancer, (ii) three or more cores with Gleason 3+4 cancer, (iii) any single core with Gleason 4+3 cancer or higher, (iv) a Gleason 3+3 at diagnosis that is upgraded to Gleason 3+4 or (v) undergoing treatment, regardless of histological progression. Although many existing active surveillance protocols incorporate volume of cancer in their definition of progression, these are based on random biopsy of the prostate. Critical volumes of cancer based on targeted biopsy have not been defined and will be explored in this analysis.

- Progression rate will be estimated for each scheduled surveillance biopsy as the proportion of study patients without prior progression for whom the biopsy indicates progression.
- Cumulative progression rate will be estimated for each of the four planned biopsies as the proportion of patients with progression among those having had all planned biopsies to date, or a previous biopsy indicating progression.

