### **10.4 Sample size, accrual rate and study duration**

We plan to accrue approximately 55 patients per year for the first three years of the study; this assumes a 10% dropout rate. The power (97.3%), is based on 150 patients, using a two-sided binomial test at the 5% significance level to detect an increase in the 24-month cumulative progression rate from 12.5%, as expected for AS historically, to 25% for MRI-AS. Enrollment will occur during the first 3.25 years. Enrollment will be completed at < 3.33 years from the enrollment of the last patient.

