## 10.5 Statistical Analysis

Descriptive statistics will be done for patient demographics and baseline disease characteristics. Counts and percentages will be used to summarize the distribution of categorical variables while median, range, mean and standard deviation will be used for continuous variables. Baseline characteristics will include age, race/ethnicity, T-stage, Gleason score, PSA, PSAD and performance status. Continuous scores will be compared using ANOVA and linear regression controlling for common demographic and clinical variables.

For each scheduled surveillance biopsy session, we will tabulate patients and the following status categories: biopsy indicating progression, biopsy negative for progression, biopsy not performed for progression detected on earlier biopsy, biopsy not performed because patient refused, or biopsy not performed because patient dropped out of study.

Time to event endpoints such as progression and BCR will be analyzed by Kaplan-Meier (KM) or competing risk (CR) methods. Where the Kaplan Meier method is used, point estimates and two-sided 95% confidence intervals for rates will be reported for selected times using Greenwood's variance and the log-log transform method. Median survival time, if attained, will also be reported. We will report the progression rate and the cumulative progression rate for each surveillance biopsy. Taking the third scheduled biopsy at the end of 2 years as illustration, the progression rate at 24 months is the proportion of biopsied patients indicating progression among the total number of biopsied patients over the 24 month period. The 24-month cumulative progression rate is the primary endpoint, which will include those who complete the first three biopsies or have progression from the first or second biopsy. The primary endpoint, 24-month cumulative progression rate, will be estimated and reported with corresponding 95% confidence intervals. Groups will be compared by the log rank test. In addition, we will report and plot the cumulative progression rates in each arm for the four scheduled surveillance biopsies. It is expected that the early difference with historical values and those obtained with MRI-guided biopsies will not be sustained; that is, the 36-month cumulative progression rates will be approximately equal. Similar estimation of time-specific and cumulative rates will be done for Histological progression.

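### The cumulative-rate rule leaves out a progression observed at 24 months if the man missed his 12-month biopsy, then counts him as a progressor at 36 months

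*Combined protocol and SAP*

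**What the plan says.** Section 7.2 schedules an initial protocol biopsy, then biopsies "and at 12, 24 and 36 month from initial biopsy". The 24-month biopsy is therefore the third, as section 10.5 confirms: "Taking the third scheduled biopsy at the end of 2 years as illustration".

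Section 10.1.1 takes the cumulative rate at each biopsy as "the proportion of patients with progression among those having had all planned biopsies to date, or a previous biopsy indicating progression". Section 10.5 restates this for the primary endpoint, "which will include those who complete the first three biopsies or have progression from the first or second biopsy". Section 10.1.2 uses the same structure for histological progression.

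For each biopsy session, section 10.5 also tabulates "biopsy not performed because patient refused", as a category separate from dropout. No section says how to count a man who misses one biopsy and attends the next. Section 10.5 adds an expectation about the later comparison with historical values: "the 36-month cumulative progression rates will be approximately equal".

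**The concern.** The rule makes inclusion depend on complete attendance, with an exception for earlier progression. The exception does not cover progression at the biopsy being analysed. Two things follow for a man who misses only the 12-month biopsy.

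- At 24 months his result is known but unused, whether it is progression or not. Observed primary events are discarded.
- At 36 months he is included if the 24-month biopsy showed progression and excluded if it did not. Inclusion then depends on the outcome, which pushes the 36-month rate up. The plotted cumulative curve can rise between 24 and 36 months simply because men re-enter.

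The first affects the primary endpoint. The second affects the plan's expectation that the early difference from historical values will have gone by 36 months. This is not the problem of permanent dropout: these men return and have a result.

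**Working it through.** **1. The plan's own figure.** Section 10.4 states: "The power (97.3%), is based on 150 patients, using a two-sided binomial test at the 5% significance level", for an increase in the "24-month cumulative progression rate from 12.5%, as expected for AS historically, to 25% for MRI-AS". With an exact binomial test and at most 2.5% in the upper tail, the null is rejected at 28 or more progressions of 150. P(X ≥ 28 | 12.5%) = 1.9% and P(X ≥ 28 | 25%) = 97.3%. The stated power reproduces. The issue is the estimator, not the power.

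**2. The rule applied to men who miss only month 12** (initial biopsy negative, so each counts as a non-progressor at the initial biopsy):

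| 24-month biopsy | 36-month biopsy | In 24-month rate? | In 36-month rate? |
|---|---|---|---|
| progression | not needed | no | yes, as progressor |
| negative | negative | no | no |
| negative | progression | no | no |

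Reading the word previous in 10.1.1 to include the current biopsy would rescue the first row at 24 months. Section 10.5 closes that route, because it names only the first or second biopsy.

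**3. A count example (assumed numbers).** Take 135 full attenders with 34 progressions by 24 months, and 15 returning skippers of whom 4 progress at 24 months.

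- 24 months: the rule gives 34/135 = 25.2%; everyone counted gives 38/150 = 25.3%.
- 36 months, with no new event: the rule gives 38/(135 + 4) = 38/139 = 27.3%; everyone counted stays at 25.3%.
- If anywhere from 0 to 15 of the skippers progress at 24 months, the rule still gives 25.2%, while the rate in all men runs from 34/150 = 22.7% to 49/150 = 32.7%.

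**4. Expected bias.** Let p1 to p4 be the rates at the four biopsies among men not yet progressed, and s the share of men at risk who skip only month 12. Assume skipping is random, all skippers return, and any progression is found at the next biopsy. Put f3 = 1 − (1−p2)(1−p3) and f4 = 1 − (1−p2)(1−p3)(1−p4).

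- All men, 24 months: p1 + (1−p1)f3
- Rule, 24 months: [p1 + (1−p1)(1−s)f3] / [p1 + (1−p1)(1−s)]
- All men, 36 months: p1 + (1−p1)f4
- Rule, 36 months: [p1 + (1−p1)(1−s)f4 + (1−p1)s·f3] / [p1 + (1−p1)(1−s) + (1−p1)s·f3]

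Scenario A uses the Miami re-biopsy rates in section 1.5.1 (7%, 18%, 17%), with 17% assumed for the fourth. Scenario B is assumed, to match the 25% alternative: 10%, 9%, 8.4%, 5%.

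Scenario B with s = 10%: f3 = 0.1664 and f4 = 0.2081.

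- All men: 0.10 + 0.90 × 0.1664 = 25.0% at 24 months, and 0.10 + 0.90 × 0.2081 = 28.7% at 36.
- Rule at 24 months: (0.10 + 0.81 × 0.1664)/0.91 = 25.8%.
- Rule at 36 months: (0.10 + 0.81 × 0.2081 + 0.09 × 0.1664)/(0.91 + 0.09 × 0.1664) = 0.2836/0.9250 = 30.7%.

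Bias in percentage points:

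| Skip share | A, 24 mo | A, 36 mo | B, 24 mo | B, 36 mo |
|---|---|---|---|---|
| 5% | +0.2 | +1.0 | +0.4 | +0.9 |
| 10% | +0.5 | +2.1 | +0.8 | +1.9 |
| 20% | +1.1 | +4.4 | +1.8 | +4.2 |

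At 10% skipping, the share of men dropped from the primary rate is 9.3% (A) or 9.0% (B), and the share of observed progressions dropped is 8.1% (A) or 6.0% (B). The 24-month bias is upward because men who progress at the initial biopsy always stay in, while the men removed carry only the remaining risk f3. A more front-loaded 25% scenario (60% of the risk at the initial biopsy) gives 27.7% against 25.0% at 20% skipping.

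**5. Effect on the primary test.** A simulation took 150 men at a true rate of 12.5%, with random skipping of month 12 only and the exact test. The upper-tail false-positive rate is 1.9% with no skipping, about 2.8% to 3.6% at 10% skipping, and 4.0% to 6.3% at 20% (equal risk per biopsy versus 60% at the initial biopsy). The nominal limit is 2.5%.

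**6. If the skipped look is lost.** Suppose a skipper is detected at 24 months only with probability p3. A rate that counts all returning men is then too low by (1−p1)·s·(f3−p3). At 10% skipping this is 0.093 × (0.3194 − 0.17) = 1.4 points in A and 0.09 × (0.1664 − 0.084) = 0.7 points in B.

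**The case against.** The other side has a fair case. Section 6.1 requires men to agree to serial MRI and biopsy, section 5.3 allows withdrawal for non-compliance, and no skip rate is given, so the affected group may be very small. At 10% skipping the 24-month shift is under 1 point in both scenarios, against a planned difference of 12.5 points and a standard error of about 3.5 points (√(0.25 × 0.75/150)). The per-biopsy rate in 10.1.1 does count the 24-month event, and 10.5 names Kaplan-Meier or competing-risk methods for progression. The Background warns that biopsy can miss the dominant tumour, so requiring equal numbers of looks is a defensible choice. Scenario A gives 36.7% at 24 months, which matches neither planning rate.

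Much of that stands, and it limits the size of the point. It does not remove it. The primary endpoint is the cumulative proportion, and neither the per-biopsy rate nor the time-to-event methods are tied to it. An equal-looks rule would also not admit returning skippers at 36 months only when they had progressed at 24.

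Some stronger readings are tempting but unsupported:

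- That skippers who do not progress are never counted. They count at the initial biopsy.
- That later inclusion simply follows progression. A skipper who first progresses at 36 months is excluded at 36 months too.
- That a man without the initial biopsy shows the same fault. Section 7.2 times every later biopsy from the first, so he has no defined 12- or 24-month biopsy.
- That the plan predicts men will refuse once and return. Section 10.5 provides for refusal at each session but does not say that refusers come back.

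**Conclusion.** The point holds as a defect in the definition of the primary estimator. Read as written, sections 10.1.1 and 10.5 discard a progression observed at 24 months in a man who missed month 12, count him at 36 months, and exclude the same man from both rates if he stays negative. Section 10.1.2 has the same structure.

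The size is modest: about +0.2 to +1.8 points at 24 months and +0.9 to +4.4 at 36 months in scenarios A and B. These figures rest on an assumed 5% to 20% skip share, random skipping, and the next biopsy finding what the skipped one would have found. If skipping is related to risk, the 24-month bias could go either way.

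A reader might infer that the primary test is invalid or the power figure wrong. The documents do not support that. The 97.3% reproduces, and the test is materially affected only if skipping is common or related to risk. The 36-month bias is larger, but that comparison is an expectation without a margin or test. The change should be made before analysis, because deciding how to count returning refusers after seeing results would be a post hoc choice on the primary endpoint.

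**What to change.** In 10.1.1, 10.1.2 and 10.5, define the cumulative rate at biopsy k as follows. Numerator: men with progression at or before biopsy k. Denominator: those men plus men without progression who had biopsy k, whether or not an earlier biopsy was skipped. Report how many men had a skipped earlier biopsy.

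Add two sensitivity analyses:

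- The rate among men with all planned biopsies or progression at or before biopsy k. This admits a returning skipper only if he progressed, so it should be read as the high side. At 10% skipping it gives 0.2498/(1 − 0.09 × 0.8336) = 27.0% against 25.0% in scenario B.
- The Kaplan-Meier or competing-risk estimate already named in 10.5. This can also use a man who skips month 24 and is negative at month 36, whom the new proportion still leaves out at 24 months.

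The cost is wording only: no new data, visits or patients. The downside to state is that skippers have had one fewer look. If that look is a lost chance of detection, the new 24-month rate is about 0.7 to 1.4 points low at 10% skipping. Permanent dropout is a separate matter that this change does not address.

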### 10.1.2 Histological progression

In the context of this trial, histological progression refers to a surveillance biopsy that indicates any one of the following: (i) more than 4 positive cores involving any grade of cancer, (ii) three or more cores with Gleason 3+4 cancer, (iii) a Gleason 3+3 at diagnosis that is upgrade to Gleason 3+4, or (iv) any single core with Gleason 4+3 cancer or higher.

- Histological progression rate will be estimated for each scheduled biopsy as the proportion of study patients without prior GS progression for whom the biopsy indicates GS progression.
- Cumulative histological progression rate will be estimated for each scheduled biopsy as the proportion of patients with histological progression among those having had all planned biopsies to date, or a previous biopsy indicating Gleason score progression.

## 10.2 Secondary Study Endpoints

### 10.2.1 Time-to-Biochemical recurrence

Biochemical recurrence (BCR) is defined as PSA of 0.2 or higher on two or more separate measures after surgery or an increase of nadir + 2ng/ml or more after radiation. Time-to-BCR is defined as duration between date of treatment and date of BCR if BCR occurs.

#### 10.2.2 QOL scores

Three contemporary instruments will be utilized to assess patient function and bother (Expanded Prostate Cancer Index Composite (EPIC), physical and mental health (SF12) and prostate cancer-specific anxiety Memorial Anxiety Scale for Prostate Cancer patients (MAX-PC). Each of these measures will be assessed via the specific scoring instructions for each instrument. Given that this is a single arm trial, we will compare patient reported quality of life to historical active surveillance cohorts to see if MRI and MR targeted biopsy of the prostate improves patient quality of life.

#### 10.2.3 Area under ROC curves as predictive measure and incremental prediction improvement for progression

Patients will be categorized at baseline by NCCN risk class ranging from very low risk to intermediate risk and into those who progressed while on the trial and those who did not. Logistic regression will be used to model the association between NCCN risk class and progression using AUC for ROC curves. The incremental benefit of mpMRI, genomic testing and molecular markers compared to NCCN risk alone will be evaluated by comparing AUC using a likelihood ratio test. MRI will be categorized from 1-5 using PIRADS, while genomic test scores and molecular markers can be used as continuous scores or categorized into levels of risk (low/ intermediate/high).

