#### **3.2 Secondary Objectives**

- 1) To identify whether earlier identification of progression with MRI and MRI-US fusion biopsy will portend improved outcomes of patients undergoing delayed primary surgery or radiation after initial surveillance at the University of Miami
- 2) To determine the effect of multiparametric MRI and MRI-US fusion biopsy on health related quality of life and cancer specific anxiety using patient reported validated questionnaires.
- 3) To determine the incremental benefit of mpMRI, genomic risk test, and molecular marker at baseline compared to NCCN risk class for predicting progression on Active Surveillance

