### 7.3 Early discontinuation of study participation

Patients who experience protocol-defined progression will have attained the primary study outcome and will undergo treatment either with radical prostatectomy or whole gland image guided radiotherapy of the prostate at the University of Miami. Their histopathology (for surgery patients) and rates of biochemical recurrence will be followed and compared to historical series for comparison with cohorts not undergoing MRI guided selection for surveillance versus immediate treatment. However, those who refuse the recommendation for treatment will continue to be followed per active surveillance standard of care guidelines. Furthermore, those who seek treatment outside UM will be contacted for information on histopathology (for those undergoing surgery) and rates of biochemical recurrence. Patient refusal of the recommendation for treatment or further follow-up beyond progression will not be a protocol deviation. Patients who are without progression upon completion of the third annual biopsy will be censored without progression.

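### The AUC analysis for secondary objective 3 uses an untimed ever/never logistic model with no rule for men whose biopsy follow-up is incomplete, so the AUC can be biased in a direction the plan leaves open

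*Combined protocol and SAP*

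**What the plan says.** Secondary objective 3 (section 3.2) asks what mpMRI, genomic testing and molecular markers at baseline add "compared to NCCN risk class for predicting progression on Active Surveillance". Section 10.2.3 is the analysis written for it. Men are divided "into those who progressed while on the trial and those who did not", and "Logistic regression will be used to model the association between NCCN risk class and progression using AUC for ROC curves". The markers are then judged by the gain in AUC over NCCN class. The section gives no time window, no minimum number of biopsies and no category for incomplete follow-up.

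Other sections bear on the same outcome:

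- **Schedule (7.2).** Biopsies are taken at baseline "and at 12, 24 and 36 month from initial biopsy".
- **Denominator (10.1.1).** The cumulative progression rate is "the proportion of patients with progression among those having had all planned biopsies to date, or a previous biopsy indicating progression". Section 10.5 applies the same idea to the 24-month primary endpoint.
- **Treatment (10.1.1, item v).** Progression includes "undergoing treatment, regardless of histological progression".
- **Missing biopsies (10.5).** The status table has separate entries for "biopsy not performed because patient refused, or biopsy not performed because patient dropped out of study". They are used for tabulation only.
- **Censoring (7.3).** "Patients who are without progression upon completion of the third annual biopsy will be censored without progression". No equivalent rule is given for men who stop sooner.
- **Methods (10.5).** Progression is named as a time-to-event endpoint for Kaplan-Meier or competing-risk analysis, with Cox regression for such outcomes. Neither is tied to the AUC analysis.
- **Dropout (10.4).** 10% is assumed.

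**The concern.** Histological progression can be seen only at a biopsy. A man with one negative biopsy who then leaves untreated has an unknown outcome at 36 months, while a man with four negative biopsies has a known one. A two-way split with no time window cannot tell them apart. The analyst must either call the first man a non-progressor or leave him out, and section 10.2.3 does not say which.

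The choice matters because the quantity of interest is an increment in AUC, which may itself be small. If the decision to skip later biopsies is related to MRI result or to another marker, part of the apparent gain, or loss, reflects who kept attending. Two analysts could follow section 10.2.3 and report different AUCs from the same data.

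**Working it through.** **The plan's own figure.** The documents give no figure for the AUC analysis. The nearest is the 97.3% power of the primary test (10.4: 150 men, 12.5% against 25%, two-sided 5%). The exact binomial test rejects in the upper tail at 28 or more events, with upper-tail error 0.0193 and power 0.9734, so that figure reproduces.

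**Inputs for the AUC check.** From the documents: four biopsies (7.2), 10% dropout (10.4), the denominator rule (10.1.1). Assumed: progression in 10% of men at the first biopsy and 9% of those still progression-free at each later one; all men have the first biopsy and progression there counts; those who leave do so straight after it, untreated.

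- Never progressing: 0.90 × 0.91³ = 0.678
- Progressing by 36 months: 1 − 0.678 = 0.322
- Progressing after the first biopsy: 0.322 − 0.100 = 0.222

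**A. Dropout unrelated to the marker, leavers coded negative.** Progressors missed: 0.10 × 0.222 / 0.322 = 6.9%. They form 0.0222 / (0.0222 + 0.678) = 3.2% of the group labelled non-progressors. If early and late progressors have the same marker distribution, a true AUC of 0.770 becomes 0.770 − 0.032 × (0.770 − 0.500) = 0.761. If the marker acts on the hazard at each biopsy, so that late progressors have less extreme values, simulation gives 0.764. The loss is about 0.006 to 0.009.

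**B. Refusal related to MRI, useless MRI (true AUC 0.50).** Assumed: 40% of men MRI-negative; 20% or 30% of them refuse later biopsies, against 5% of MRI-positive men. Overall refusal is 0.4 × 0.20 + 0.6 × 0.05 = 11%, or 0.4 × 0.30 + 0.6 × 0.05 = 15%. Observed progression is 0.10 + (1 − refusal) × 0.222: 0.311 in MRI-positive men, and 0.277 or 0.255 in MRI-negative men. For a binary marker, AUC = 0.5 + ½ × [P(MRI+ | progressor) − P(MRI+ | non-progressor)].

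| Refusal, MRI− v MRI+ | P(MRI+) in observed progressors | P(MRI+) in non-progressors, leavers coded negative | AUC | P(MRI+) in non-progressors, leavers excluded | AUC |
|---|---|---|---|---|---|
| 20% v 5% | 0.627 | 0.589 | 0.519 | 0.640 | 0.493 |
| 30% v 5% | 0.646 | 0.581 | 0.532 | 0.671 | 0.488 |

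The last column is the complete-case rule of 10.1.1. The sign reverses, and the bias is roughly a third as large.

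**C. Continuous marker, leaving spread over the three later biopsies.** Simulation of 1,000,000 men per scenario. Cumulative progression is 10/18/25/30% at 0/12/24/36 months: 25% is the design rate in 10.4, about 30% comes from the centre's own cohort in 1.4.1, and the other two are assumed. The log-odds of refusal change by −1, 0 or +1 per SD of the marker (assumed). True AUC 0.70:

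| Dropout | Coding | Low-marker men refuse more | Unrelated | High-marker men refuse more |
|---|---|---|---|---|
| 10% | leavers negative | 0.707 | 0.695 | 0.671 |
| 10% | complete case | 0.682 | 0.699 | 0.712 |
| 30% | leavers negative | 0.724 | 0.686 | 0.628 |
| 30% | complete case | 0.644 | 0.699 | 0.745 |

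At 10% dropout, 3-8% of true progressors are missed. Inverse-probability-of-censoring weights returned the true value within simulation error throughout. Refusal there depended only on the marker, and the true weights were used.

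**The case against.** A reader might infer that the plan codes leavers as negatives and so inflates the AUC of MRI. The documents do not support that. Section 10.2.3 is silent, and where the plan does define a denominator (10.1.1, repeated in 10.5) it excludes men with incomplete biopsies, which reverses the sign. Nor would every man who stops biopsy be coded negative, since those who leave for treatment are progressors under item v. The idea that a reassuring MRI leads to refusal is plausible but appears nowhere in the documents, and entry requires agreement to serial MRI and biopsy (6.1). All of this stands, so no direction can be claimed.

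It can also be said that follow-up has a natural end at the 36-month biopsy, so logistic regression on a fixed window is an ordinary choice. That is fair for men who complete the schedule, but it does not classify those who do not.

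On size, 30% progression among 230 men is 69 progressors and 161 others. The standard error of a null binary-marker AUC is then ½ × √(0.24/69 + 0.24/161) = 0.035, so the shifts in B lie within one standard error. That also stands, but bias does not shrink with sample size and cannot be seen in the result. The calculations use stand-alone AUCs rather than the increment over NCCN class, so they indicate scale only.

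Finally, one sentence adopting the 10.1.1 rule would be cheaper. It would essentially remove the bias from unrelated dropout, but not the bias from marker-related refusal.

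**Conclusion.** The point holds in a limited form. Section 10.2.3 specifies a method that takes no account of censoring, for an outcome the plan elsewhere treats as time-to-event, and does not say what happens to men who refuse or drop out untreated. Refusal related to a marker biases its AUC under either coding, with opposite signs. Unrelated dropout biases it only under the literal coding.

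At the planned 10% dropout the effect is modest: 0.006 to 0.009 for a true AUC of 0.770 if dropout is unrelated, and up to about 0.03 with the strong assumed link in C. At 30% dropout it reaches about 0.07. These sizes rest on assumed progression timing and refusal patterns. What is firm is that the plan leaves the coding, and with it the sign of any bias, undecided for the one analysis written for secondary objective 3. It should be changed before the analysis; the primary endpoint is not affected.

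**What to change.** In section 10.2.3:

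1. Define progression by fixed horizons of 24 and 36 months from the initial biopsy.
2. Replace the ever/never logistic model with a discrete-time hazard model by biopsy number (for example with a complementary log-log link), in which each man contributes only the biopsies he had. Keep treatment as progression, as in 10.1.1.
3. Report AUC at each horizon with inverse-probability-of-censoring weights. The weight model should include NCCN class, MRI category and each marker being tested, since refusal could be related to any of them.
4. Report the leavers-as-negative and complete-case codings as sensitivity analyses, with numbers refused and dropped out by MRI category.

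The cost is SAP wording, somewhat more analysis work and slightly wider intervals. No new data are needed, because section 10.5 already has biopsy status classified at each session. The weights do not correct refusal driven by unmeasured factors, and the report should say so.
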